## **8.5 Subgroup analyses**

One pre-specified subgroup analysis of the primary outcome will be undertaken.

### **8.5.1 Treatment preferences**

Since it is not possible to blind participants to their treatment/allocation and the primary outcome was self-reported, it is plausible that treatment preferences at baseline may influence PEM responses during follow up. The data collected on treatment preferences at baseline will be used to divide participants into three subgroups based on their actual allocation; allocated to preferred treatment, not allocated to preferred treatment and no preference. PEM scores at 12 months post-treatment will be analysed using a univariate linear regression model with fixed effect terms for allocation, reference joint and baseline PEM score and a random intercept for recruitment site, with main effects of preference subgroup (allocated to preferred treatment group, not allocated to preferred treatment group, no treatment preference) and the interaction of this term with allocation being added as fixed effects. This will be compared with the model without this interaction using a likelihood ratio test (both models will be fitted using maximum likelihood). Should this test suggest improvement in model fit at the 10% level, then the model including the preference subgroup main effect and interaction will be used to derive estimates of the treatment effect at 12 months in each preference subgroup together with two sided 95% CIs.

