### **6.1 Treatment preferences**

Participants are asked about their treatment preferences at baseline. Participants indicate whether they would prefer to receive collagenase, limited fasciectomy or have no preference. The baseline CRF is clear that their response to this question will have no impact on their chances of receiving a particular treatment. This data will be used as part of a subgroup analysis to explore possible treatment effect heterogeneity due to receipt (or otherwise) of the preferred treatment.

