## Appendix E-2 – Primary Outcome Reporting

**Table xx:** Descriptive summaries of PEM scores over time

	Collagenase (N = )	Surgery (N = )	Total (N = )
Baseline			
N			
Mean (SD)			
Median (Q1, Q3)			
Min, Max			
Pre-treatment			
N			
Mean (SD)			
Median (Q1, Q3)			
Min, Max			
Month 3			
N			
Mean (SD)			
Median (Q1, Q3)			
Min, Max			
Month 6			
N			
Mean (SD)			
Median (Q1, Q3)			
Min, Max			
Month 12			
N			
Mean (SD)			
Median (Q1, Q3)			
Min, Max			
Month 24			
N			
Mean (SD)			
Median (Q1, Q3)			
Min, Max			

**Table xx:** Estimated differences in mean PEM scores over time for each of the planned analyses of the primary outcome (except the analyses exploring sensitivity to outcome data being missing not at random)

	Estimated difference (95% CI)
Unadjusted analysis	
Baseline	-
Pre-Treatment	
3 Months	
6 Months	
12 Months	
24 Months	
Primary analysis	
3 Months	
6 Months	
12 Months (primary endpoint)	
24 Months	
Sensitivity analysis including baseline predictors of missingness	
3 Months	
6 Months	
12 Months	
24 Months	
Sensitivity analysis using multiply imputed data	
3 Months	
6 Months	
12 Months	

24 Months	
Sensitivity analysis adjusting for treatment delivery measurement	
3 Months	
6 Months	
12 Months	
24 Months	
Sensitivity analysis using data collected within planned follow up window*	
3 Months	
6 Months	
12 Months	
24 Months	
Sensitivity analysis adjusting for diathesis	
3 Months	
6 Months	
12 Months	
24 Months	
Complier Averaged Causal Effect Analysis	
12 Months	
Subgroup analysis	
Received preferred treatment	
Did not receive preferred treatment	
No treatment preference	

\*The specified timeframes are as follows. Pre-treatment PEM completed within 18 weeks of randomisation, month 3 and month 6 PEM completed within +/-14 days of 3 and 6 months post treatment, month 12 and month 24 PEM completed within +/- 3 months of 12 and 24 months post treatment.

**Table xx:** Sensitivity analysis exploring departures from MAR.

$\Delta$ (sensitivity parameter)	Imputing assuming $\Delta = \delta$ in which arm?	Estimated Difference (95% CI)
$\delta = 0$	Collagenase arm only	
	Surgery arm only	
	Both arms	
$\delta = 1$	Collagenase arm only	
	Surgery arm only	
	Both arms	
$\delta = 2$	Collagenase arm only	
	Surgery arm only	
	Both arms	
$\delta = 3$	Collagenase arm only	
	Surgery arm only	
	Both arms	
$\delta = 4$	Collagenase arm only	

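### The preference subgroup is defined by whether allocation matched preference, so its interaction test partly measures prognosis and rejects only at its 10% size for a symmetric match effect

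*SAP*

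**What the plan says.** Section 6.1 records preference at baseline in three categories: "Participants indicate whether they would prefer to receive collagenase, limited fasciectomy or have no preference". It says the data will be used to "explore possible treatment effect heterogeneity due to receipt (or otherwise) of the preferred treatment".

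Section 8.5 limits subgroup work to a single analysis: "One pre-specified subgroup analysis of the primary outcome will be undertaken". Section 8.5.1 motivates it by the lack of blinding and the self-reported outcome. It then uses the preference data to "divide participants into three subgroups based on their actual allocation; allocated to preferred treatment, not allocated to preferred treatment and no preference". The 12-month PEM model contains allocation, reference joint, baseline PEM and a random site intercept, plus the main effect of this three-level factor and "the interaction of this term with allocation being added as fixed effects". For the test: "This will be compared with the model without this interaction using a likelihood ratio test". The condition for going further is: "Should this test suggest improvement in model fit at the 10% level". Only then are treatment effects estimated in each subgroup.

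Appendix E-2 prints these three estimates in the same table as the primary result. One of the rows is labelled "Did not receive preferred treatment".

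**The concern.** A subgroup factor should be fixed before randomisation, so that the two arms are comparable within each level. Match status is a function of both preference and allocation. In the matched group every collagenase participant preferred collagenase and every surgery participant preferred surgery; in the unmatched group it is the reverse. The difference between arms in either group therefore mixes the treatment effect with any difference in outlook between the two kinds of patient.

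Two errors could follow. A significant result could reflect prognosis alone, and the derived subgroup effects would then be read as randomised estimates beside the primary result. A non-significant result could be read as reassurance that unblinded patients' preferences did not affect the outcome, when the test did not examine the most natural form of that influence.

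**Working it through.** **Inputs.** From SAP section 3: effective N = 568, SD = 22, margin 6. From section 8.5.1: a likelihood ratio test at 10%; with a three-level factor the interaction has 2 df. Assumed, because the SAP gives no preference split: collagenase/surgery/none of 33/33/34, 50/10/40, 60/20/20, 25/25/50 and 70/5/25, with 1:1 allocation within each.

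**The SAP's own figure.** 2 × 22² × (1.960 + 1.282)² / 6² = 282.5, so 283 per arm by the normal approximation. The t-test with 284 per arm has 90.05% power, and 568 / 0.8 = 710. The stated sample size is reproduced. The SAP states no power for the subgroup test.

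**What the interaction contains.** Write μ(A,p) for the mean under allocation A (C or S) in people with preference p (c, s or n).

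- Matched difference: μ(C,c) − μ(S,s). Unmatched difference: μ(C,s) − μ(S,c).
- Matched minus unmatched: [μ(C,c) + μ(S,c)] − [μ(C,s) + μ(S,s)]. This is twice the prognostic difference between collagenase-preferrers and surgery-preferrers. No treatment effect appears in it.
- Average of the two differences: ½{[μ(C,c) − μ(S,c)] + [μ(C,s) − μ(S,s)]}. Set against the no-preference effect, this is genuine heterogeneity and forms the second degree of freedom.

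**Where a symmetric match effect goes.** In the model without interaction, with match main effects γm and γu, the collagenase-surgery effect is τ − (γu − γm) in c, τ + (γu − γm) in s and τ in n. A symmetric penalty γu − γm is fitted perfectly by that model. It is in both models being compared, so the test rejects only at its size.

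**Rejection rates** (noncentral chi-square, 2 df, critical value 4.605; pC, pS are the proportions preferring collagenase and surgery).

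1. Prognostic gap D only, no treatment effect anywhere. The matched difference is −D and the unmatched +D if surgery-preferrers do worse. Noncentrality λ = N·h·D²/SD², with h = pC·pS/(pC + pS).
   - 33/33/34: h = 0.165; D = 6 gives λ = 568 × 0.165 × 36 / 484 = 6.97, rejection 76%.
   - 70/5/25: h = 0.0467; D = 6 gives λ = 1.97, rejection 33%.
   - Over the five splits: D = 3, about 16-30%; D = 6, 33-76%; D = 8, 50-94%. A test of baseline preference by allocation stays at 10% throughout.
2. Symmetric 8-point penalty (effects −8/+8/0 in c/s/n).
   - SAP test: λ = 0, rejection 10% for every split. In simulation a symmetric 12-point effect gave 10.1% and 10.4% at two splits.
   - Baseline-preference test: λ = N·Var(effect)/(4·SD²). At 33/33/34, 568 × 42.24 / 1936 = 12.4, power 94%. At 70/5/25, 568 × 20.96 / 1936 = 6.15, power 71%.
3. One-sided 8-point penalty (collagenase-preferrers allocated surgery only).
   - 33/33/34: 56% for both tests.
   - 70/5/25: the SAP weights are 568/2 × 0.0467 = 13.25 for each of the matched and unmatched groups and 568 × 0.25/4 = 35.5 for no preference. The differences are 0, −8 and 0, so λ = 1.38 and rejection is 26%. The baseline-preference test has λ = 568 × 0.7 × 0.3 × 64 / 1936 = 3.94 and power 54%.
   - If the penalty instead falls only on the 5% who preferred surgery, the SAP λ is unchanged (26%), while the baseline-preference test has λ = 568 × 0.05 × 0.95 × 64 / 1936 = 0.89 (21%). The SAP's small excess there comes through the prognostic contrast, so a rejection could not be read as heterogeneity.

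**The case against.** A reader might infer that the test has no power for any preference-driven heterogeneity, or that the real interaction is never tested. Neither follows. The preference-by-allocation interaction has 2 df; one is hidden in the match main effect and the other is in the tested term. A 12-point effect shared by both preference groups but absent in those with none is detected in 59-90% of trials, against 75-90% with baseline preference as the factor. One-sided penalties are also detected, as shown above.

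The prognostic gap must survive adjustment for baseline PEM and reference joint, and nothing in the SAP suggests that a large gap would. An 8-point gap exceeds the margin itself; at 3 points the excess over 10% is modest. This limits the size of the false-positive problem but does not remove it, and it has no bearing on the 10% result for symmetric effects.

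The full model is saturated in the six allocation-by-preference cells, so valid within-preference contrasts could be recovered from the same fit. That is true, but the SAP plans neither to test nor to report them.

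Finally, section 6.1 describes the aim as exploratory, and section 8 bases non-inferiority on the primary model's confidence interval. This stands and sets the severity.

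**Conclusion.** The factor and the tested term in section 8.5.1 do not match the aim in section 6.1. The matched and unmatched estimates are not randomised comparisons. If treatment had no effect and surgery-preferrers did 8 points worse, they would be centred on −8 and +8, both outside the 6-point margin. Half of the tested interaction is prognostic. A symmetric effect of getting or missing the preferred treatment, the main pattern the aim implies, is flagged in 10% of trials whatever its size.

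The algebra and the 10% result need no assumption about splits or SD. The other rates rest on N = 568, SD 22 and the assumed splits. SD 22 is a baseline figure without covariate adjustment; a smaller residual SD raises the rates (for an 8-point gap at 50/10/40, 72% at SD 22 and 83% at SD 19).

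This should be fixed, but it does not undermine the trial's main conclusion: the primary estimate and the non-inferiority decision are untouched.

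**What to change.** In section 8.5.1, define the subgroup by baseline preference (collagenase, surgery, none). Fit its main effect and its interaction with allocation, keeping the other terms, and test the 2-df interaction by the same likelihood ratio test. Report the 12-month collagenase-surgery difference with its 95% CI within each baseline-preference group; each is then a randomised comparison.

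If a single summary of the match effect is also wanted, test the match term in a model that adjusts for baseline preference.

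Relabel the three subgroup rows in Appendix E-2 by baseline preference. This also removes the mismatch between those rows, which speak of treatment received, and section 8.5.1, which speaks of allocation.

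The cost is SAP wording only: the data are already collected, and the six cells, the number of parameters and the software are unchanged. If few participants prefer one treatment, the interval in that group will be wide (5% of 568 is about 28 people), and the report should say so.

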## **3. Sample size**

The primary outcome for DISC is the score obtained for the 11 items in part two of the PEM at 12 months post treatment. Previous survey data collected from a representative sample of 880 patients with Dupuytren's Contracture showed the standard deviation of the scores for the 11 items in part 2 of

the PEM at baseline to be 22 points (unpublished). We estimate that a 6 point difference on the PEM at 12 months post-treatment is the threshold at which differences become relevant to the patient, and represents an appropriate non-inferiority margin. An effective sample size of 568 participants (284 per arm) is required to obtain 90% power to assess non-inferiority of collagenase based on the upper limit of a two sided 95% confidence interval (CI) (equivalent to a one-sided 97.5% CI) for the treatment difference ( $\delta = \text{collagenase} - \text{surgery}$ ) at 12 months post treatment, assuming a non-inferiority margin of 6 points and a standard deviation of 22 points. This calculation is based upon the sample size needed for 90% power in a one-sided independent samples t-test of size 2.5%, of  $H_0: \delta \geq 6$  vs  $H_1: \delta < 6$ , ignoring informative baseline covariates (reference joint and baseline PEM score). If  $\delta = 6$ , then we would expect the null hypothesis that collagenase is inferior to surgery to be rejected in 2.5% of hypothetical repetitions of the trial. If  $\delta = 0$ , then we would expect the null hypothesis that collagenase is inferior to surgery to be (correctly) rejected in 90% of hypothetical repetitions of the trial (assuming an analysis based on a one sided independent samples t-test of size 2.5%). Assuming 20% attrition at the 12 month follow up, the total target sample size is 710.

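### SAP 8.5.1 reports preference-subgroup effects only if the interaction test passes at 10%, conflicts with its own results table, and forms groups that do not isolate heterogeneity by preference

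*SAP*

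**What the plan says.** Section 8.5 announces one subgroup analysis of the primary outcome. Section 8.5.1 motivates it by the lack of blinding and the self-reported outcome, and forms "three subgroups based on their actual allocation; allocated to preferred treatment, not allocated to preferred treatment and no preference". A model for 12-month PEM includes allocation, subgroup and their interaction. "This will be compared with the model without this interaction using a likelihood ratio test".

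The next step is conditional: "Should this test suggest improvement in model fit at the 10% level, then the model including the preference subgroup main effect" and interaction is used to "derive estimates of the treatment effect at 12 months in each preference subgroup together with two sided 95% CIs". The section does not say what is reported when the test does not pass.

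Two other places differ. The Appendix E-2 table of planned primary-outcome analyses has a row for each of the three subgroups with no condition attached, and one of them reads "Did not receive preferred treatment". Section 6.1 describes the aim as exploring "treatment effect heterogeneity due to receipt (or otherwise) of the preferred treatment". Both speak of receipt, while 8.5.1 speaks of allocation.

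**The concern.** Three things are wrong together.

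- **Selection on significance.** Estimates appear only when they look heterogeneous. A test that does not pass at 10% does not show equal effects, and with wide subgroup intervals the reader needs to see those intervals. When estimates do appear, their spread is inflated on average.
- **Text against table.** When the test does not pass, 8.5.1 gives no estimates and Appendix E-2 has empty rows for them. An analyst cannot follow both. The SAP expects departures from allocation (the crossover variable in Table 3, the CACE analysis in 8.3.3), so grouping by treatment received and by allocation would give different groups.
- **What the groups measure.** Each preference subgroup in 8.5.1 takes its two arms from people with opposite preferences. Removing the condition while keeping those groups would publish contrasts that do not answer the question in 6.1.

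At stake is the only analysis aimed at a bias that the SAP itself names. The primary non-inferiority conclusion is not affected.

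**Working it through.** **The plan's own figure.** Section 3 states: "An effective sample size of 568 participants (284 per arm) is required to obtain 90% power", "assuming a non-inferiority margin of 6 points and a standard deviation of 22 points". The normal approximation, n per arm = 2 × (1.960 + 1.282)² × 22² / 6², gives 283. The noncentral t gives power 0.8995 at 283 and 0.9005 at 284, so 284 is right. 568 / 0.8 = 710 also agrees. The SAP gives no power, preference split or expected interaction size for the subgroup test.

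**Precision of a subgroup effect.** Assume equal thirds (568 / 3 = 189.3) and 1:1 within each. SE = 22 × √(4 / 189.3) = 3.20, so the 95% CI is about ±6.3 points. The gap between two subgroups has SE 3.20 × √2 = 4.52 and a CI of about ±8.9.

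**Chance of passing the test.** With two preferences plus none, the interaction has 2 degrees of freedom; the 10% critical value is 4.605. Take subgroup effects of −3, 0 and +3, a gap equal to the 6-point margin, which is the only relevance benchmark in the SAP. Noncentrality = (9 + 0 + 9) / 3.20² = 1.76, and the test passes with probability 0.307. Simulation, keeping only the trials that pass, gives the mean reported gap.

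| Assumed split and SD | SE, preference subgroups | Passes | Mean gap when reported (truth 6) |
|---|---|---|---|
| Equal thirds, SD 22 | 3.20 | 31% | 10.5 |
| 25/25/50, SD 22 | 3.69 | 26% | 11.5 |
| Equal thirds, 3:1 preference ratio, SD 22 | 3.69 | 26% | 11.5 |
| Equal thirds, SD 18 | 2.62 | 40% | 9.2 |

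The third row is needed because 1:1 within the preference subgroups is not guaranteed: their arm ratio follows the ratio of collagenase-preferrers to surgery-preferrers. At 3:1 the two arms have about 142 and 47 people, and SE = 22 × √(1/142 + 1/47.3) = 3.69.

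With no gap at all (equal thirds, SD 22), 10% of trials still report subgroup effects, with a mean absolute gap of 7.3 points. For larger true gaps (same assumptions) the selection fades: at 10 points the test passes in 62% and the reported gap averages 1.26 times the truth; at 15 points, 91% and 1.05 times.

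**What the gap measures.** Write C and S for people preferring collagenase and surgery, and m(C, coll) and so on for their mean 12-month PEM by arm, adjusted for the other covariates.

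- Effect among those allocated to their preference: A = m(C, coll) − m(S, surg).
- Effect among those not allocated to it: B = m(S, coll) − m(C, surg).
- A − B = [m(C, coll) + m(C, surg)] − [m(S, coll) + m(S, surg)], which is twice the prognostic difference between C and S, averaged equally over arms.

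The treatment effects in C and S cancel out of A − B. Their difference goes into the subgroup main effect: half the sum of the two cells in the first group, minus half the sum in the second, equals half of (effect in C − effect in S). The other degree of freedom compares the average effect in C and S with the effect in the no-preference group.

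Two checks at equal thirds, SD 22:

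- A 3-point prognostic difference with no heterogeneity gives subgroup effects 6 points apart and a 31% pass rate, exactly the first row of the table.
- True effects of −10 in C, +10 in S and 0 in the no-preference group, with equal prognosis, give A = B = 0 and a 10% pass rate. Grouped by stated preference, the same truth passes in 99%.

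**The case against.** The strongest defence is that requiring a positive interaction test is a common guard against over-reading subgroups, that 10% is lenient, and that there is only one such analysis. The aim is fair, but the method does not serve it: the wide, honest intervals are withheld and those selected for apparent heterogeneity are released. Reporting everything with the interaction p-value and a caution gives the same protection without selection.

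It can also be said that Appendix E-2 already provides the rows, and that receipt there and in 6.1 is loose wording, since 8.5.1 is the operative text and section 8 sets intention-to-treat principles. The label point alone is indeed minor. The missing condition is a real conflict, because text and table lead to different reports.

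A reader might infer that real preference-by-treatment heterogeneity will usually go unreported and that whatever is reported is exaggerated. The SAP does not support either in that form. It states no split and no interaction size. Over the range examined (splits from 40/40/20 to 15/15/70, SD 22 or 19.1), the pass rate reaches 50% at gaps of about 7 to 13 points. Exaggeration is an average, not true of every estimate: at a true 6-point gap, 88% to 92% of reported gaps exceed it. And under the grouping in 8.5.1, the gap between the two preference subgroups is not treatment-effect heterogeneity at all.

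**Conclusion.** The point holds as a matter of selective reporting, internal conflict and subgroup definition. At a 6-point gap, with 568 analysed, the 10% condition withholds the estimates in roughly 60% to 74% of trials and inflates the mean reported gap to between 9.2 and 11.5 points. These figures rest on assumed splits, arm ratios and SDs, and the effect is smaller for larger gaps. The definition problem needs no such assumptions: it follows from the algebra. Two of the three subgroup effects compare people with opposite preferences and are not randomised comparisons, so it is not enough to delete the condition or to relabel the table rows by allocation. The change should be made, but nothing here bears on the primary analysis.

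**What to change.** 1. In 8.5.1, delete the 10% condition. Report the 12-month effect with its two-sided 95% CI in every subgroup, and the interaction p-value whatever its size, labelled exploratory, with a statement that a non-significant test does not show equal effects.
2. Define the subgroups by stated baseline preference (collagenase, surgery, none) and test preference by allocation. Each subgroup effect is then a randomised comparison.
3. Align the wording of 6.1, 8.5.1 and the Appendix E-2 row labels with that definition, not with treatment received.

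The cost is SAP text and a recoded subgroup variable. Preference is already collected at baseline, and an interaction model is fitted in any case for the likelihood ratio test.
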